4.2 Phase I Dose Escalation Scheme

Dose escalation will be performed independently for each arm and three to six patients will be enrolled per dose in each arm. A standard “3+3” dose escalation design will be utilized. Accrual will be staggered by two weeks between the first and second patients in a dose level. If one of three patients suffers a dose limiting toxicity (DLT), then accrual of the next three patients will also be staggered by two weeks each. However, staggering will not be required for accrual of additional patients to define the MTD at the next lowest dose level or at level 3 if no DLT is experienced in first three patients. **Table 1** below presents a summary of the dose escalation schema.

Table 1 – Dose Escalation Schema			
Cohort	Number NSCs Injected	Total Viral Dose (vp/patient)	Number of Subjects
1	50 million (5 x 10 ⁷)	6.25 x 10 ¹⁰	3-6
2	100 million (1 x 10 ⁸)	1.25 x 10 ¹¹	3-6
3	150 million (1.5 x 10 ⁸)	1.875 x 10 ¹¹	3-6

Three dose levels as described above will be tested. The two arms will be dose-escalated independently. Once the MTD is determined or after six subjects are evaluated and found to tolerate dose level 3 (the highest dose), the Phase I study will end and the results will be reviewed. The appropriate dose for a future Phase II study will be the highest administered or maximum tolerated dose from the Phase I study. Dose escalation decision rules are found in **Table 2** below.

Table 2 – Dose Escalation and Stopping Rules	
Number of Patients with DLT At a Given Dose Level	Escalation Decision Rule
0 out of 3	Enter 3 patients at the next dose level
≥ 2	Dose escalation will be stopped. Three additional patients may be entered, after discussion with the sponsor, at the next lowest dose level if only three patients were treated previously at that dose.

1 out of 3	Enter three more patients at this dose level. If none of these three additional patients experience a DLT, then dose escalation occurs, unless this is the highest dose, in which case dose escalation is stopped and the highest dose is declared the MTD. If 1 or more of these additional 3 patients have a DLT, then three additional patients may be entered, after discussion with the sponsor, at the next lowest dose level if only three patients were treated previously at that dose.
Highest dose level without \geq DLT	This will be recommended Phase II dose.

NOTE: Whichever dose level is declared the MTD must have 6 total patients treated at that level. For example, if 3 patients are treated at level 2 and 0 patients experience DLT, escalation would then proceed to level 3. However, if \geq 2 patients at level 3 experience DLT, enrollment to level 2 would need to be re-opened to enroll an additional 3 patients at that level (with 0 or 1 DLT observed in 6 total patients) in order to declare level 2 the MTD.

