4.2.1 Definitions of Dose-limiting Toxicities

- Subjects will be evaluated for dose-limiting toxicities (DLT period) from the time of signing informed consent through completion of concomitant radiation and temozolomide.
 - DLTs will be evaluated using CTCAE v 4.03 criteria
 - The DLT will be defined as any of the following:
 - Toxicity attributed to study product
 - Any grade 3 toxicity including hematologic and non-hematologic toxicities
 - Any grade 3 toxicity related to the intervention requiring interruption or delay in radiation therapy for more than seven days except CNS hemorrhage*
- * Grade 3 (asymptomatic) radiologic evidence of CNS hemorrhage (commonly seen after biopsy) is not a DLT. Grade 4 (symptomatic) CNS hemorrhage is a DLT. Assessment of neurological toxicity relates to the relative changes from the pre-treatment neurological status. Other anticipated toxic phenomena that are not related directly to viral transduction of the brain tumor or neurological complications which can be explained by the presence of the mass lesion and are compatible with the natural history of malignant brain tumors may require cessation of treatment in individual patients. Such occurrences would not be considered DLT unless they occur with a greater frequency than expected in this patient population.
- A safety analysis will take place 14 days after the first and second subjects receive treatment, and before moving to the next higher viral dose level. The DMC will assess the safety of administering NSC-CRAd-S-pk7 in future patients either at the same dose or a modified dose. No patients will receive treatment until the DMC provides their recommendation.
 - The maximally tolerated dose is defined as the dose level immediately below the dose where the DLT was observed.

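### Table 2, its NOTE, the MTD definition in Section 4.2.1 and the stated minimum of 9 per arm disagree on how many patients the declared dose needs

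*Combined protocol and SAP*

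**What the plan says.** Five parts of the plan bear on how many patients must have been treated at the dose finally named.

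- **Table 2, toxicity rows (Section 4.2).** With two or more DLTs at a level, escalation stops, and the table adds: "Three additional patients may be entered, after discussion with the sponsor, at the next lowest dose level if only three patients were treated previously". The row for one DLT in three uses the same permissive wording: "If 1 or more of these additional 3 patients have a DLT, then three additional patients may be entered, after discussion with the sponsor".
- **NOTE below Table 2.** "Whichever dose level is declared the MTD must have 6 total patients treated at that level". Its worked example is level 2 passed at 0/3 followed by toxicity at level 3. Level 2 then has to be re-opened for three more patients, "with 0 or 1 DLT observed in 6 total patients) in order to declare level 2 the MTD".
- **Section 4.2.1.** The MTD is the dose level directly under the one at which DLT was seen. No patient number is attached.
- **Phase II dose.** The last row of Table 2 says "This will be recommended Phase II dose" and gives no patient count. The text of Section 4.2 says "The appropriate dose for a future Phase II study will be the highest administered or maximum tolerated dose from the Phase I study". Sections 6.1 and 10.2 treat the MTD and the recommended Phase II dose as the same thing.
- **Sample size (Study Summary and Section 10.2).** If all three levels are used, each arm enrols 9 to 18 patients; Section 10.2 gives 18 to 36 in total.

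For the top level, Section 4.2 does fix a number: "after six subjects are evaluated and found to tolerate dose level 3 (the highest dose), the Phase I study will end".

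**The concern.** The MTD is the primary endpoint, and Section 10.3.2.2 sends the reader to Section 4.2 for the algorithm that determines it. The common case is an arm that passes a level at 0/3, escalates, and stops for toxicity at the next level. For that case the plan says three things about the lower level: three more patients may be added (Table 2), six are required before it can be called the MTD (NOTE), and it is already the MTD (Section 4.2.1).

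If the expansion is not done, following Section 4.2.1 gives an MTD on three patients, and following the NOTE gives no MTD. The plan does not say which result would be reported. The two arms escalate independently, so they could even be handled differently.

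**Working it through.** **1. The plan's own figure.** Table 10 gives the chance of escalating past a level. Under the 3+3 rule, P(escalate) = (1−p)³ + 3p(1−p)² × (1−p)³.

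| True DLT rate p | Plan | Recomputed |
|---|---|---|
| 20% | 71% | 70.9% |
| 30% | 49% | 49.4% |
| 40% | 31% | 30.9% |
| 50% | 17% | 17.2% |
| 60% | 8% | 8.2% |

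Table 10 reproduces. It concerns escalation only, so it does not depend on the lower-level expansion.

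**2. The stated sample size.** To reach level 3, levels 1 and 2 must each pass with 3 patients (0/3) or 6 patients (1/3, then 0/3).

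- Stated minimum: 3+3+3 = 9. No level has six.
- With the NOTE applied and level 3 tolerated: 3+3+6 = 12.
- With the NOTE applied, level 3 rejected after three patients, and level 2 expanded: 3+6+3 = 12.
- Maximum either way: 6+6+6 = 18.

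Under the NOTE the range is therefore 12 to 18 per arm and 24 to 36 in total, against the stated 9 to 18 and 18 to 36.

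**3. How often the decision arises.** The documents give no DLT rates by level, so the rates below are assumptions. For rates p₁, p₂, p₃, write A(p) = (1−p)³ for 0/3, E(p) for the escalation probability in step 1, and L(p) for at most 1 DLT in 6. Level 3 is taken to six patients, as Section 4.2 requires, so it is rejected with probability 1 − L(p₃). An arm stops with only three patients at the level below with probability

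A(p₁)[1−E(p₂)] + E(p₁)A(p₂)[1−L(p₃)].

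- 5/10/20%: 0.8574 × 0.0939 + 0.9734 × 0.7290 × 0.3446 = 0.0805 + 0.2446 = **32.5%**
- 10/20/30%: 0.7290 × 0.2914 + 0.9061 × 0.5120 × 0.5798 = 0.2124 + 0.2690 = **48.1%**
- 10/20/40%: 0.2124 + 0.9061 × 0.5120 × 0.7667 = 0.2124 + 0.3557 = **56.8%**

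**4. What three and six patients show.** One-sided 95% Clopper-Pearson upper limits on the DLT rate:

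- 0/3: 1 − 0.05^(1/3) = 63%
- 0/6: 1 − 0.05^(1/6) = 39%
- 1/6: 95th percentile of Beta(2, 5) = 58%

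The chance that a level passes on 0/3 alone is (1−p)³. The chance that it passes on 0/3 and then at most one DLT in the next three is (1−p)³ × [(1−p)³ + 3p(1−p)²].

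| True DLT rate | 0/3 only | 0/3, then ≤1/3 | Share of 0/3 passes the expansion would reject |
|---|---|---|---|
| 40% | 21.6% | 14.0% | 35% |
| 50% | 12.5% | 6.3% | 50% |

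**The case against.** The best defence is that the passages can be read together. Expansion is optional, but without it no MTD is declared. Sections 6.1 and 10.2 make the Phase II dose the MTD, so the six-patient rule carries over to it. The NOTE's example is exactly the disputed case, and Section 4.2 separately requires six at level 3. The phrase allowing the highest administered dose follows that sentence and most naturally means level 3 tolerated in six.

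Much of this stands, and it rules out several stronger readings:

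- A reader might infer from the last row of Table 2 that the plan deliberately lets a Phase II dose rest on three patients. That needs the row to be read alone. The row also appears to have lost a number after its inequality sign, so little can rest on it.
- A reader might infer that the expansion is left to the sponsor's sole discretion. The text says only that it follows discussion with the sponsor.
- A reader might see a conflict between sponsor and DMC, because Section 4.2.1 says "No patients will receive treatment until the DMC provides their recommendation". That section has the DMC consider dosing at the same or a modified dose, and discussion with the sponsor can take place as well. Both can be followed.
- A reader might take 32.5% to 56.8% as the frequency of three-patient doses. That would need the chance that expansion is declined, which the documents do not give.

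The statistical gain from expansion is also uneven: the upper limit falls only from 63% to 58% if one DLT appears among the six.

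The defence does not dispose of the point. It leaves the MTD definition in Section 4.2.1 unexplained, since that definition carries no patient number. It also leaves the minimum of 9. That figure can be reached if level 3 is rejected after three patients and level 2 is not expanded, but under the NOTE such an arm ends without an MTD, and Section 10.2 does not say so.

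**Conclusion.** The inconsistency is real and lies in the rules that fix the primary endpoint. For an arm that passes a level at 0/3 and stops for toxicity above it, the text supports a three-patient MTD under Section 4.2.1, or no MTD under the NOTE if the optional expansion is not done. The stated minimum is 3 per arm and 6 in total below what the NOTE implies when all three levels are used.

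The sample-size result and the confidence limits need no assumed DLT rates. The frequencies do, and they rest on three illustrative sets of rates; they show that the situation would be common, not that a three-patient dose would be. The documents do not establish that a three-patient Phase II dose is intended.

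**What to change.** Bring these passages into agreement: the two toxicity rows and the last row of Table 2, the NOTE, the Phase II dose sentence in Section 4.2, and the MTD definition in Section 4.2.1. One patient-number requirement should apply to both the MTD and the Phase II dose, since Sections 6.1 and 10.2 equate them.

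State what is reported for an arm in which the lower level is not expanded, including when the DMC advises against it. Say whether the DMC hold in Section 4.2.1 covers that expansion. Complete the last row of Table 2 if a number is missing from the source.

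If the NOTE's six-patient requirement is kept, restate the minimum in the Study Summary and Section 10.2 as 12 per arm, and the total in Section 10.2 as 24 to 36. The maximum of 18 per arm and Table 10 do not change.

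The cost in that case is a higher stated minimum and loss of the option to stop at three patients and still name a dose.

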10.2 Sample Size and Accrual

This phase 1 study is not powered to detect statistically significant differences in efficacy. The primary endpoint of this Phase I dose-escalation study is the MTD of NSC-CRAd-S-pk7 when administered with standard radiation and chemotherapy in patients with malignant glioma. The 3+3 design has a 71% chance (49%, 17%) of dose escalating when the true toxicity rate for that dose is 20% (30%, 50%).

If all three dose levels are administered, the minimum number of patients enrolled will be 9 per arm and the maximum number of patients will be 18 per arm, for total accrual of 18-36 patients enrolled. Based upon the dose escalation schema described, groups of three to six patients will be entered at a dose level in each arm. Using this algorithm, the probabilities of dose escalation for various true DLT rates are given in Table 10. For example, if the true DLT is 50% at a dose level, there is a 17% chance that the dose would be escalated. The maximum tolerated dose determined in this study will be the recommended dose for a Phase II study. In the event the final pathology reading reveals anything other than a malignant glioma, such a patient will not be counted as one of the minimum number required without DLT for advancement to the next dose level but will be counted if a DLT is experienced.

Table 10– Probabilities of Dose Escalation	
20%	71%
30%	49%
40%	31%
50%	17%
60%	8%

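### When the highest dose level is passed, Table 2 and sections 4.2, 4.2.1, 6.1 and 10.2 do not agree on what the MTD is, and no path shows an upper limit of tolerability

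*Combined protocol and SAP*

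**What the plan says.** Section 4.2 sets the design: "A standard “3+3” dose escalation design will be utilized", with three levels and each arm escalated on its own. What it says about level 3 is spread over several places.

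- **Table 2, row for 1 of 3.** Three more patients are entered. If none has a DLT, escalation follows unless this is the highest dose, "in which case dose escalation is stopped and the highest dose is declared the MTD".
- **Table 2, row for 0 of 3.** "Enter 3 patients at the next dose level". There is no exception for level 3, which has no next level.
- **Table 2, last row.** The highest level below some DLT threshold becomes the recommended Phase II dose. The threshold number is missing in the text available for review, possibly through the PDF reading.
- **Section 4.2, staggering sentence.** It foresees "additional patients to define the MTD at the next lowest dose level or at level 3 if no DLT is experienced in first three patients".
- **Section 4.2, end of study.** "Once the MTD is determined or after six subjects are evaluated and found to tolerate dose level 3", the study ends.
- **Section 4.2, Phase II dose.** "The appropriate dose for a future Phase II study will be the highest administered or maximum tolerated dose from the Phase I study".
- **NOTE under Table 2.** Any level declared the MTD needs six treated patients. The worked example, for level 2, accepts 0 or 1 DLT among the six.
- **Section 4.2.1, last bullet.** The MTD is the level one step under the dose at which the DLT was seen.
- **Section 6.1.** The primary endpoint equates the MTD with the recommended Phase II dose.
- **Section 10.2.** "The maximum tolerated dose determined in this study will be the recommended dose for a Phase II study".

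Section 10.3.2.2 refers the primary analysis back to 4.2 and 4.2.1 and adds no tie-breaker.

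**The concern.** Level 3 can be passed, with at most one DLT in six, in three ways: (A) 1/3 then 0/3; (B) 0/3 then 0/3; (C) 0/3 then 1/3. A and C are the same data in a different order. Table 2 attaches the term MTD only to A, and section 4.2.1 disagrees with it there.

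Two things are at stake. First, the label on the primary endpoint could depend on the order of events or on which section the analyst follows, and the two arms could be labelled differently on identical totals. Second, on A, B and C alike no dose has been rejected. Reporting level 3 as the MTD would then tell a Phase II team that a toxicity limit was found, when the trial only reached its last planned dose.

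**Working it through.** **Step 1: the plan's own figures.** Table 10 in section 10.2 gives the chance of escalating at a true DLT rate p. With P(escalate) = (1−p)³ + 3p(1−p)² × (1−p)³, a rate of 20% gives 0.512 + 0.384 × 0.512 = 0.709. Rates of 30, 40, 50 and 60% give 0.494, 0.309, 0.172 and 0.082. The plan states 71, 49, 31, 17 and 8%. Table 10 reproduces, so the problem is not in the operating characteristics.

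**Step 2: the label each place gives.**

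| Level 3 result | Table 2 | Staggering sentence and NOTE | Section 4.2.1, literally |
|---|---|---|---|
| A: 1/3 then 0/3 | Level 3 is the MTD | 1 of 6, would qualify | Level 2 |
| B: 0/3 then 0/3 | No explicit MTD label | 0 of 6, would qualify | No MTD if no DLT at any level |
| C: 0/3 then 1/3 | No explicit MTD label | 1 of 6, would qualify | Level 2 |

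Section 4.2.1 could be read more kindly, taking the DLT to mean the stopping criterion of two or more. On A no level meets that criterion, so the definition then yields no MTD. On either reading it does not return the level 3 that Table 2 declares.

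**Step 3: chance of each path, given that level 3 is reached and filled to six.** P(A) = P(C) = 3p(1−p)⁵ and P(B) = (1−p)⁶. The documents give no expected DLT rate, so p is an assumption.

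| p at level 3 | A | B | C | Total (0 or 1 of 6) | A as share of total |
|---|---|---|---|---|---|
| 5% | 11.6% | 73.5% | 11.6% | 96.7% | 12% |
| 10% | 17.7% | 53.1% | 17.7% | 88.6% | 20% |
| 20% | 19.7% | 26.2% | 19.7% | 65.5% | 30% |
| 30% | 15.1% | 11.8% | 15.1% | 42.0% | 36% |

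A and C are equally likely. If both arms end at 1/6 on level 3, Table 2 labels them differently with probability 2 × 0.5 × 0.5 = 50%.

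**Step 4: a whole arm.** Multiply by the chance of escalating through levels 1 and 2.

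| Assumed DLT rates, levels 1/2/3 | Reach level 3 | Pass level 3 (A+B+C) | By path A only | By B or C |
|---|---|---|---|---|
| 5/5/5% | 94.8% | 0.9476 × 0.9672 = 92% | 0.9476 × 0.1161 = 11% | 81% |
| 10/10/10% | 82.1% | 0.8211 × 0.8857 = 73% | 0.8211 × 0.1771 = 15% | 58% |
| 5/10/20% | 88.2% | 0.8821 × 0.6554 = 58% | 0.8821 × 0.1966 = 17% | 40% |

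**Step 5: what the data can show.** On all three paths every level tested has stayed below two DLTs and nothing above level 3 has been tried. The result bounds any MTD from below, at level 3, and not from above. Even 1/6 is imprecise: its exact 95% confidence interval for the DLT rate is 0.4% to 64%.

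**The case against.** A reader might infer from Table 2 that 0/6, or 0/3 then 1/3, leaves the arm with no MTD, so that a cleaner result is treated worse than a more toxic one. The documents do not support that. The staggering sentence provides for more patients at level 3 after 0/3, expressly to define the MTD. The NOTE opens with a general six-patient requirement and offers level 2 only as an example; its criterion of 0 or 1 in six ignores order. The end-of-study sentence says when the trial stops, not which label applies, and tolerating level 3 may simply mean meeting that criterion.

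A reader might also infer that the primary endpoint is mislabelled or that the wrong dose goes forward. That does not follow either. Section 4.2 admits the highest administered dose as the Phase II dose. Table 2's last row points the same way: it covers 0/6 under any threshold, and 1/6 in either order if the missing number is 2. The dose carried forward is probably level 3 on all three paths. It can also be said that reserving the term MTD for a level with a rejected dose above it is a matter of terminology.

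These points stand, and they limit the finding to inconsistent definition and labelling. They do not remove it. The helpful sentences are an aside on staggering and an example; neither amends the 0/3 row, both sit uneasily with section 4.2.1, and sections 6.1 and 10.2 drop the highest-administered alternative.

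**Conclusion.** The concern holds as an inconsistency in the rule for the primary endpoint. The clearest contradiction is between Table 2 and section 4.2.1: for 1/3 then 0/3 at level 3, one declares level 3 and the other, read literally, gives level 2. Alongside it, Table 2 has no explicit MTD label for 0/6 or for 0/3 then 1/3, and the Phase II dose wording in 4.2 differs from that in 6.1 and 10.2.

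It matters because passing level 3 is the likeliest end of an arm if toxicity is low: about 92%, 73% and 58% of arms under the three assumed sets of rates, with only 11%, 15% and 17% reaching it by the labelled path. These figures assume independent DLTs, Table 2 followed at levels 1 and 2, and six counted patients at level 3. They count arms whose label is open to argument, not arms in which a different dose would be chosen. On every such path the supportable statement is that no dose tested was found too toxic. The change should be made before the primary endpoint is reported. Table 10 is unaffected.

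**What to change.** - Reconcile section 4.2 with Table 2 and its NOTE, section 4.2.1, section 6.1 and section 10.2 to a single MTD definition, stated once and cross-referenced. It should depend on the six-patient total and not on the order of events. Which dose rule applies is for the sponsor to settle.
- Give Table 2 an explicit level 3 entry for 0 of 3 and for each six-patient total, and make sure the threshold in its last row is legible.
- Report separately the case in which no dose was found too toxic, for example as *MTD not reached; highest dose tested*.
- Use the same Phase II dose wording in 4.2, 6.1 and 10.2.

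This is a wording change. It needs no patients beyond the six already required at any level declared the MTD. Section 10.2's minimum of 9 per arm is 3 + 3 + 3; an arm that ends with six at level 3 needs at least 3 + 3 + 6 = 12, which follows from the existing NOTE and not from this change. The downside is a less favourable conclusion in the arms concerned.

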4.2.1 Definitions of Dose-limiting Toxicities

- Subjects will be evaluated for dose-limiting toxicities (DLT period) from the time of signing informed consent through completion of concomitant radiation and temozolomide.
 - DLTs will be evaluated using CTCAE v 4.03 criteria
 - The DLT will be defined as any of the following:
 - Toxicity attributed to study product
 - Any grade 3 toxicity including hematologic and non-hematologic toxicities
 - Any grade 3 toxicity related to the intervention requiring interruption or delay in radiation therapy for more than seven days except CNS hemorrhage*
- * Grade 3 (asymptomatic) radiologic evidence of CNS hemorrhage (commonly seen after biopsy) is not a DLT. Grade 4 (symptomatic) CNS hemorrhage is a DLT. Assessment of neurological toxicity relates to the relative changes from the pre-treatment neurological status. Other anticipated toxic phenomena that are not related directly to viral transduction of the brain tumor or neurological complications which can be explained by the presence of the mass lesion and are compatible with the natural history of malignant brain tumors may require cessation of treatment in individual patients. Such occurrences would not be considered DLT unless they occur with a greater frequency than expected in this patient population.
- A safety analysis will take place 14 days after the first and second subjects receive treatment, and before moving to the next higher viral dose level. The DMC will assess the safety of administering NSC-CRAd-S-pk7 in future patients either at the same dose or a modified dose. No patients will receive treatment until the DMC provides their recommendation.
 - The maximally tolerated dose is defined as the dose level immediately below the dose where the DLT was observed.

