4.6.3 Chemotherapy

Standard of care TMZ will be administered concurrent with radiotherapy (75mg/m²). Patients will sign a drug calendar daily indicating that they have completed the daily TMZ dose during the XRT/TMZ phase (weeks 2 through 7).

Four weeks later, TMZ will be given (150mg/m² for the first cycle then escalated in the absence of > grade 1 hematotoxicity to 200mg/m² if tolerated) during each cycle for a total of 6 cycles. A cycle will consist of 5 days “on”/23 days “off” per Stupp protocol. Dose delays or modifications will be according to the literature at the discretion of the treating oncologist as this is a standard of care treatment.

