7.2.2 Severity of AEs

All non-hematologic adverse events will be graded according to the NCI Common Terminology Criteria for Adverse Events (CTCAE) version 4.03. The CTCAE v4 is available at <http://ctep.cancer.gov/reporting/ctc.html>

If no CTCAE grading is available, the severity of an AE is graded as follows:

- Mild (grade 1): the event causes discomfort without disruption of normal daily activities.
- Moderate (grade 2): the event causes discomfort that affects normal daily activities.
- Severe (grade 3): the event makes the patient unable to perform normal daily activities or significantly affects his/her clinical status.
- Life-threatening (grade 4): the patient was at risk of death at the time of the event.
- Fatal (grade 5): the event caused death.

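### Both graded DLT items say grade 3 without 'or higher', so on the more plausible reading most product-related Grade 4-5 events are literally not counted

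*Combined protocol and SAP*

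**What the plan says.** Section 4.2.1 calls a DLT any of the items that follow. Those items are, in order:

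- an attribution line that carries no grade: "Toxicity attributed to study product"
- a general item with a grade but no mention of cause: "Any grade 3 toxicity including hematologic and non-hematologic toxicities"
- a radiation-delay item, again with a single grade: "Any grade 3 toxicity related to the intervention requiring interruption or delay in radiation therapy for more than seven days except CNS hemorrhage"

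The footnote to the last item exempts asymptomatic radiologic hemorrhage at Grade 3 and adds that "Grade 4 (symptomatic) CNS hemorrhage is a DLT". No other grade above 3 appears in the definition. Section 10.3.2.2 refers back to Section 4.2.1 and adds no threshold of its own.

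Table 2 in Section 4.2 acts on the DLT count at each level. For 0 of 3 the instruction is "Enter 3 patients at the next dose level". With 1 of 3 the cohort is expanded to six, and with two or more escalation stops. The result is the MTD, which Sections 6.1 and 10.2 make both the primary endpoint and the Phase II dose.

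**The concern.** Read literally, a criterion of grade 3 is not a criterion of Grade 3 and above. Elsewhere the protocol writes a threshold or a range when it means one. In Section 4.6.3 temozolomide is "escalated in the absence of > grade 1 hematotoxicity", and Section 8.1.10 on the study product describes earlier toxicity as Grades 3 and 4. The fallback severity scale in Section 7.2.2 gives Grade 4 its own line, "Life-threatening (grade 4): the patient was at risk of death at the time of the event", apart from Grades 3 and 5.

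The rule turns on one or two patients, so a single uncounted event can change its instruction. The events at risk of being missed are the most severe ones, in a study whose only formal decision is the dose to carry forward.

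**Working it through.** **1. The two possible layouts.** The indentation of the list is not preserved in the machine-read text, so two readings must be compared.

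| | Attribution line is a heading | Attribution line is its own item |
|---|---|---|
| Product-related Grade 1-2 | not a DLT | DLT |
| Product-related Grade 3 | DLT, apart from the hemorrhage exemption | DLT |
| Product-related Grade 4-5, not CNS hemorrhage | literally not a DLT | DLT |
| Grade 3 not due to the product | not a DLT | DLT, unless the clause on anticipated and natural-history events applies |

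The heading reading is the more plausible. The flat one would make a trivial product-related event dose-limiting. It could also count temozolomide cytopenias, which the temozolomide side-effects section lists at Grade 3 to 4 with at least 10% incidence and which fall inside the DLT window. Against the heading reading, a lead-in promising several alternatives followed by one top-level entry is awkward. The radiation-delay item adds little under either layout, so it does not help to choose.

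**2. Effect on Table 2 under the heading reading, with no assumed rate.** Take three patients at a level, where the affected patients have a product-related Grade 4 event other than CNS hemorrhage and no separate Grade 3 event.

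- Two affected: intended count 2, stop; literal count 0 of 3, escalate.
- One affected: intended count 1 of 3, add three patients; literal count 0 of 3, escalate.

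Both trial-level stops in Section 10.3.2.2 require more than two patients, and one covers neurologic toxicity only. Two affected patients alone trigger neither.

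**3. The plan's own operating figures.** With true DLT rate p and q = 1 − p, Table 2 gives

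P(escalate) = q³ + 3pq² × q³ = q³ + 3pq⁵.

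- p = 0.20: 0.512 + 0.197 = 0.709
- p = 0.30: 0.343 + 0.151 = 0.494
- p = 0.40: 0.216 + 0.093 = 0.309
- p = 0.50: 0.125 + 0.047 = 0.172
- p = 0.60: 0.064 + 0.018 = 0.082

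These match the 71, 49, 31, 17 and 8% of Table 10.

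**4. Illustration only.** Let s be the share of DLT patients whose only qualifying events are uncounted Grade 4-5 events. The documents give no value, so s is an assumption. The counted rate is p(1 − s), put into the same formula, before any committee intervenes.

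| s | p = 0.50: counted rate → escalate | p = 0.20: counted rate → escalate |
|---|---|---|
| 0 | 0.50 → 17% | 0.20 → 71% |
| 0.1 | 0.45 → 23% | 0.18 → 75% |
| 0.2 | 0.40 → 31% | 0.16 → 79% |
| 0.3 | 0.35 → 40% | 0.14 → 83% |
| 0.4 | 0.30 → 49% | 0.12 → 87% |

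**The case against.** The strongest reply is that the consequence depends on list formatting. Read flat, the attribution line already makes every product-related Grade 4 or 5 event a DLT. That stands: the effect on the count is conditional.

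The second reply is intent. The footnote's statement that Grade 4 hemorrhage counts fits best if Grade 4 is otherwise in scope. Section 8.1.10 also reports a Grade 4 thrombocytopenia treated as a DLT in an earlier adenovirus trial. That evidence is weak, since it comes from another trial's definition and that patient also had a Grade 3 event. Even so, nothing suggests that an investigator would count Grade 3 and ignore Grade 4. This shows the wording is a slip; it does not supply the missing words.

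Third, a symbol may have been lost. The sign for at least survives in Sections 3.1 and 4.2, including Table 2. One row of Table 2, however, shows the sign with no number after it, so a loss cannot be excluded.

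Fourth, a reader might infer that the trial would in fact escalate after two life-threatening events. The documents do not support that:

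- Section 4.2.1 requires a safety analysis before each higher dose and says "No patients will receive treatment until the DMC provides their recommendation".
- Section 7.0 has the DSMB review complications of the therapy before anyone new is enrolled, and halts enrollment for any death within 56 days.
- Radiation starts on day 10 to 14 and lasts about 42 days, so the DLT window closes near day 52 to 56. The death hold therefore covers most of the Grade 5 risk.
- Section 7.3.3.1 sends all serious events to the DMC.

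These safeguards make escalation unlikely. They work by judgment and leave the DLT count as it is.

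**Conclusion.** The wording defect is real: neither graded item reaches above Grade 3, and no other section extends them. Under the heading reading, product-related Grade 4-5 events other than Grade 4 CNS hemorrhage fall outside the count, and two such patients in three are recorded as 0 of 3. Under the flat reading they count, but the definition is then too broad at the low end. Either way the text needs correcting.

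Two stronger conclusions do not follow. Table 10 is not wrong; it reproduces exactly and describes the intended design, provided every intended DLT is counted. The 23 to 49% escalation figures at a true rate of 50% are not estimates for this trial: they rest on assumed shares and leave out the committee reviews.

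This should be fixed. Confidence is high for the wording and moderate for its effect on the count.

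**What to change.** In both graded items of Section 4.2.1, change grade 3 to *Grade 3 or higher (including Grades 4 and 5)*. State explicitly whether the line on toxicity attributed to the study product is the heading that governs those items. The sponsor has to make that choice, because declaring it a heading would narrow the definition if a flat list was meant.

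Keep the radiation-delay item, the exemption for asymptomatic CNS hemorrhage and the natural-history clause. Table 2 and Table 10 need no change on this account.

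The cost is a short wording amendment and a matching update to the DLT form, with no added patients or procedures.
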